### ***6.2 Study flow***

**Figure 1-3** illustrate the study flow.

**First arm (*primary objective - figure 1*):** Adnexal mass scanned at 11-14 weeks. If the decision is to manage the adnexal mass conservatively, the patient is to be re-scanned once more: 0 - 90 days postpartum. In addition, the patient will be asked to enter into the third arm of the study (see below) knowing that she can opt out from that arm at any point. If she consents to participate in the third arm, she will participate in a series of longitudinal examinations as described for the third arm.

All patients with a mass detected before 11 weeks will also be scanned at 11-14 weeks and can enter all three arms of the study. In this scenario, if more than one scan is performed during pregnancy before 11 weeks, only the first of several scans before 11 weeks will be included for the second and third arms of the study (see below).

**Second arm (*secondary objective - figure 2*):** Adnexal mass is seen for the first time during that pregnancy at any gestation. If the decision is to manage the adnexal mass conservatively, the patient is to be re-scanned once more: 0 - 90 days postpartum. For patients with a mass detected before 11 weeks, see also above (they will be re-scanned at both 11-14 weeks and at 0-90 days postpartum).

In addition, the patient will be asked to enter into the third arm of the study (see below) knowing that she can opt out from that arm at any point. If she consents to this, she will participate in a series of longitudinal examinations as described for the third arm.

**Third arm (*secondary objective - figure 3*):** Patients from the first and second arms who agree to enrol into the third arm i.e. longitudinal examination of an adnexal mass during pregnancy. For the purposes of the longitudinal evaluation, the time points for the ultrasound examination are:

- initial presenting scan if <11 weeks;
- 11-14 weeks;
- 16 week scan - endometriomas ONLY;
- second trimester routine scan (18-22 weeks);
- 30-34 weeks;
- any additional scans during pregnancy which resulted in either conservative management with extra scans or surgical intervention (with reason for the extra scan or for surgery documented);
- 0-90 days postpartum.

***If the decision is to operate after the scan at which the mass was first detected during pregnancy with no follow-up scans planned before surgery, the patient is included in the study with the final outcome being the histopathological diagnosis of the surgically removed mass (see next section).***

***If the adnexal mass is not seen at a subsequent follow-up scan but has been replaced with a normal ovary, there is no need for further follow-up scans. The final outcome is benign.***

***Patients enrolled into the study but who suffer miscarriage, ectopic pregnancy or intra-uterine death can be included in the study using same criteria as above.***

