#### **Definition of final outcome**

***The final outcome, for the purpose of the analysis, will be based on the pathology result after surgery. If surgery is not performed, the diagnosis assigned by the ultrasound examiner using subjective assessment at the 0-90 days postpartum scan will be used. If neither surgery nor a postpartum scan are performed, the final outcome is defined as 'uncertain'. We describe this in more detail below.***

The final outcome will be benign or malignant (borderline or invasive) and will be based on:

***1) Histological diagnosis of the mass, if surgery performed during pregnancy OR within 120 days of the postpartum ultrasound scan***

If surgery is performed more than 120 days after the postpartum scan the histological diagnosis will be the final diagnosis only if the histological outcome is benign.

If surgery is performed before a scheduled postpartum scan, there is no need for a postpartum scan for the purpose of the study.

***2) If no surgery performed - subjective assessment of the ultrasound image by the ultrasound examiner at postpartum scan:***

The subjective assessment of the mass will include:

- A: Benign or Malignant (borderline or invasive)

- B: Probability of malignancy (level of certainty / confidence with the diagnosis as being benign or malignant and managing it as that):

1 = benign

2 = probably benign

3 = uncertain/not possible to classify

4 = probably malignant (borderline / invasive)

5 = malignant (borderline / invasive);

- C: *Self impression*: presumed histological diagnosis (e.g. dermoid, serous cystadenoma, endometrioma, decidualised endometrioma, abscess...);

- D: *Management*: conservative management with ultrasound follow-up, surgery by general gynaecologist, surgery by oncological surgeon, other.

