***The final outcome is defined as described below***

- Ovary normal at postpartum scan, then **outcome** = benign
- Not operated on and level of certainty/confidence at postpartum scan = 1-2, then **outcome** = benign
- Not operated on and level of certainty/confidence at postpartum scan = 5, then **outcome** = malignant
- Not operated on and level of certainty/confidence at postpartum scan = 3-4, then **outcome** = uncertain
- Operated and histology = benign, then **outcome** = benign (even if surgery > 120 days after postpartum scan)
- Operated within 120 days since postpartum scan and histology = malignant, then **outcome** = malignant
- Operated > 120 days since postpartum scan AND histology = malignant AND level of certainty/confidence at postpartum scan is 4-5, then **outcome** = malignant
- Operated > 120 days since postpartum scan AND histology = malignant AND level of certainty/confidence at postpartum scan is 1-3, then **outcome** = uncertain
- Neither surgery nor postpartum scan (within 0-90 days) performed, then **outcome** = uncertain.

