**Management data**

- Suggested management: “What type of management do you propose for this patient based on ultrasound subjective assessment?”
  - Conservative management with one further ultrasound performed 0-90 days post-partum;
  - Conservative management with longitudinal follow-up as specified in the protocol (third arm of study - if patient consents to this);
  - Conservative management but with additional scans to the one listed in third arm of study with reason (pop-up: change in morphology, change in size, suspicion of malignancy; symptoms; other: specify);
  - Surgery by a gynaecologist or general surgeon;
  - Surgery by an oncological surgeon;
  - Mass is no longer present and only a normal ovary is seen - end of follow-up and completion of study;
  - Other, specify.

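### A mass that resolves to a normal ovary during pregnancy is labelled both benign and uncertain when no surgery and no postpartum scan follow

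*Protocol*

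**What the plan says.** Four parts of the protocol bear on a mass that disappears during pregnancy.

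- **Section 6.2, paragraph on masses not seen at follow-up.** If a normal ovary has taken the place of the mass, "there is no need for further follow-up scans. The final outcome is benign". No postpartum scan is made a condition.
- **Appendix 3, management data on the in-pregnancy follow-up form.** One option reads "Mass is no longer present and only a normal ovary is seen - end of follow-up and completion of study".
- **Section 6.2, descriptions of the first and second arms.** Every woman managed conservatively is to be scanned again 0-90 days postpartum. For masses found before 11 weeks, the second-arm text asks for both the 11-14 week scan and the postpartum scan. No exception is made for a resolved mass.
- **Section 6.2, Definition of final outcome.** "If neither surgery nor a postpartum scan are performed, the final outcome is defined as" uncertain. The itemised list repeats this in its last line: "Neither surgery nor postpartum scan (within 0-90 days) performed" leads to uncertain. The only line that credits a normal ovary begins "Ovary normal at postpartum scan". The definition does waive the postpartum scan for one group: "If surgery is performed before a scheduled postpartum scan, there is no need for a postpartum scan for the purpose of the study". It has no matching waiver for resolved masses.

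**The concern.** The final outcome is the reference standard for the primary outcome (the false discovery rate of ADNEX at 11-14 weeks) and for every other accuracy measure in section 7. Here it is fixed in two ways for the same woman. A centre that follows the resolved-mass paragraph and the Appendix 3 option may stop scanning and record a completed, benign case. An analyst who codes the outcome from the itemised list would label that case uncertain.

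The conflict touches only masses replaced by a normal ovary. If uncertain cases were left out of the analysis, the loss would run in one direction, with benign masses removed and no malignant ones. The situation is foreseeable. Section 2 says that most cysts seen in the first trimester have gone by 18-20 weeks, and section 6.2 states that "All patients with a mass detected before 11 weeks will also be scanned at 11-14 weeks", so some masses may be found resolved at that scan.

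**Working it through.** **Step 1: apply each rule to one woman.** Take a mass with ADNEX variables recorded at 12 weeks, conservative management, a normal ovary at the 18-22 week scan, no surgery, and no scan 0-90 days postpartum.

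- Resolved-mass paragraph (6.2): benign, scanning ends.
- Appendix 3 form: study completed.
- Opening statement of the outcome definition: no surgery and no postpartum scan, so uncertain.
- Itemised list: the normal-ovary line needs a postpartum scan, so it does not apply. The lines for unoperated women need a certainty score from the postpartum scan, so none applies. The lines for operated women do not apply. Only the last line fits: uncertain.

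The two labels differ, and no sentence says which prevails. The pointer to the next section in this part of 6.2 belongs to the paragraph on immediate surgery, not to the resolved-mass paragraph.

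**Step 2: who is affected.** If the woman has the postpartum scan and the ovary is normal, the list gives benign, in agreement with the resolved-mass paragraph. If she is operated on, the histology lines apply. The conflict therefore needs resolution in pregnancy, no surgery and no postpartum scan.

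- *Primary outcome:* she must also have an 11-14 week result and a later scan in pregnancy. That scan comes from the third arm, which she enters "knowing that she can opt out from that arm at any point", or from an added clinical scan.
- *Any-time-point secondary outcomes:* a mass found before 11 weeks and gone at the 11-14 week scan also qualifies, but again only if the scheduled postpartum scan does not take place.

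**Step 3: reproduce the planning figures (section 8, 40% threshold).** Inputs: 15 women per centre per year, 19 centres, 3 years, prevalence 8%, sensitivity 73%, specificity 95.8%.

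- N = 15 × 19 × 3 = 855; malignant = 0.08 × 855 = 68.4; benign = 786.6
- True positives = 0.73 × 68.4 = 49.93; false positives = 0.042 × 786.6 = 33.04
- False discovery rate (FDR) = 33.04 / 82.97 = 39.8%
- 95% half-width = 1.96 × √(0.398 × 0.602 / 82.97) = 10.5 points; the protocol states 11%

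The plan's figure is reproduced, and the contradiction does not make it wrong.

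**Step 4: sensitivity to lost cases.** This is an illustration. The counts k are assumptions, and so is the exclusion of uncertain cases.

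If k resolved masses that ADNEX had called malignant are lost, FDR = (33.04 − k) / (82.97 − k):

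| k | FDR |
|---|---|
| 1 | 39.1% |
| 2 | 38.3% |
| 3 | 37.6% |
| 5 | 36.0% |

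Each lost case lowers FDR by 0.7 to 0.8 points. Losing five lowers it by 3.9 points, about a third of the planned precision of 11%.

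If all the lost masses were ADNEX-negative, FDR stays at 39.8% and specificity = 1 − 33.04 / (786.6 − k). This gives 95.5% for k = 50 and 95.2% for k = 100, both within the planned precision of 1%.

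**The case against.** The strongest reply is that the text nearly answers the question itself. The resolved-mass paragraph is a specific rule in the same section, just before the general definition. It states the label outright, and the Appendix 3 option agrees with it. The last line of the list can be read as a residual category for women with no outcome information. On that reading there is one label, benign, and only a cross-reference is missing. This is a plausible account of the intent, but nowhere is it stated. The definition spells out its waiver for women operated on early and gives none for resolved masses.

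A second reply is that only the optional third-arm scans are dropped and the postpartum scan remains due. The arm descriptions support this, but the Appendix 3 option treats the study as complete. The postpartum form in Appendix 4 carries its own copy of that option, so the Appendix 3 entry does not look misplaced. This reply shows a further disagreement within the protocol about whether the postpartum scan is still due.

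The objection stands on scope and size. A reader might infer that every mass found before 11 weeks and gone at 11-14 weeks is caught. It is not, because section 6.2 schedules the postpartum scan for those women and having it removes the conflict. A reader might also infer a material bias in the primary outcome. The documents give no count for any link in that chain. Clearly physiological cysts under 5 cm are excluded, and section 2 says that resolution is much less frequent above 5 cm or in complex masses. Large assumed resolved shares, or resolved masses that are ADNEX-positive as often as other benign masses, have no support in the protocol.

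**Conclusion.** The contradiction is certain on the wording. A woman whose mass is replaced by a normal ovary during pregnancy, with neither surgery nor a 0-90 day postpartum scan, is benign under one part of section 6.2 and uncertain under another. Women who have the postpartum scan are not affected.

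The consequence is not quantified by the protocol and is probably modest. It rests on three unknowns: how many women fall in this group, how many of their masses ADNEX called malignant, and whether uncertain cases are excluded. The last may be settled in the statistical analysis plan, which was not available for this check. Any loss would be of benign masses only. It would lower FDR if some were ADNEX-positive, and otherwise would lower specificity slightly. The sample size and stated precision are not called into question. Figures 1-3, which illustrate the study flow, could not be seen. Even if they favour one rule, the conflicting sentences would remain. The point should be fixed because it concerns the reference standard and the correction is nearly free.

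**What to change.** Reconcile the arm descriptions and the resolved-mass paragraph in section 6.2, the definition of final outcome with its itemised list, and the Appendix 3 option, so that one label applies. The sponsor must choose between two routes.

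- **If the resolved-mass paragraph states the intent:** add a line to the list giving benign for a woman with no operation, no postpartum scan, and a normal ovary in place of the mass at a follow-up scan in pregnancy. Limit both statements of the uncertain category to women without such a scan. Note the exception where the arms schedule the postpartum scan. Since the new line applies only when neither surgery nor a postpartum scan has taken place, any histology or postpartum scan that is obtained still follows the existing lines.
- **If the postpartum scan is meant to be required:** amend the resolved-mass paragraph and the Appendix 3 option to say so, and leave the list as it stands.

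Either route costs a few sentences and no extra patients. The first needs no extra visits and no form changes. The second changes one form option and holds centres to a scan that the arm descriptions already schedule.

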#### **Definition of final outcome**

***The final outcome, for the purpose of the analysis, will be based on the pathology result after surgery. If surgery is not performed, the diagnosis assigned by the ultrasound examiner using subjective assessment at the 0-90 days postpartum scan will be used. If neither surgery nor a postpartum scan are performed, the final outcome is defined as 'uncertain'. We describe this in more detail below.***

The final outcome will be benign or malignant (borderline or invasive) and will be based on:

***1) Histological diagnosis of the mass, if surgery performed during pregnancy OR within 120 days of the postpartum ultrasound scan***

If surgery is performed more than 120 days after the postpartum scan the histological diagnosis will be the final diagnosis only if the histological outcome is benign.

If surgery is performed before a scheduled postpartum scan, there is no need for a postpartum scan for the purpose of the study.

***2) If no surgery performed - subjective assessment of the ultrasound image by the ultrasound examiner at postpartum scan:***

The subjective assessment of the mass will include:

- A: Benign or Malignant (borderline or invasive)

- B: Probability of malignancy (level of certainty / confidence with the diagnosis as being benign or malignant and managing it as that):

1 = benign

2 = probably benign

3 = uncertain/not possible to classify

4 = probably malignant (borderline / invasive)

5 = malignant (borderline / invasive);

- C: *Self impression*: presumed histological diagnosis (e.g. dermoid, serous cystadenoma, endometrioma, decidualised endometrioma, abscess...);

- D: *Management*: conservative management with ultrasound follow-up, surgery by general gynaecologist, surgery by oncological surgeon, other.

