## **6. METHOD and DATA COLLECTION**

### ***6.1 General Process***

We plan an initial recruitment period of 36 months. Women will be recruited to p-IOTA if found to have an adnexal mass (either newly diagnosed or previously known) at an ultrasound examination performed **at any gestational age**.

Patients will be managed as per local clinical guidelines specific to the case, with all clinical decisions taken by lead clinicians according to current policy and practice. If a patient consents to taking part in the study, the number of scans will be determined by the p-IOTA protocol.

For patients managed surgically, no follow-up ultrasound examinations after surgery will be required. Follow-up for these women is arranged by their clinicians as per clinical practice.

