### Complications from the mass during pregnancy?

Yes/No (pop up list) with number of episodes (one pop up per episode):

- Acute pain
- Chronic pain
- Suspected torsion
- Pelvic infection
- Cyst rupture with haemorrhage (ultrasound diagnosis)
- Cyst rupture without haemorrhage (ultrasound diagnosis)
- Underwent surgery for a mass-related incident but mass not removed  
    If Yes - type of surgery and findings:
  - Other, please specify: ....

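### Any surgery waives the postpartum outcome scan, even if it yields no histology, and the outcome list then has no line for the woman

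*Protocol*

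**What the plan says.** Two places in the protocol waive later scans after surgery. Section 6.1 says: "For patients managed surgically, no follow-up ultrasound examinations after surgery will be required". The definition of final outcome in section 6.2 repeats this for the scan that supplies the reference outcome: "If surgery is performed before a scheduled postpartum scan, there is no need for a postpartum scan for the purpose of the study". Neither requires that the mass was removed or that histology was obtained.

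The scan-based outcome is available only to unoperated women: "If no surgery performed - subjective assessment of the ultrasound image by the ultrasound examiner at postpartum scan". The nine-line list that follows keeps this split:

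- The three lines based on the examiner's certainty score are restricted to unoperated women, for example "Not operated on and level of certainty/confidence at postpartum scan = 1-2".
- The four lines for operated women all need a histology result, for example "Operated and histology = benign".
- The closing line, which assigns uncertain, reads "Neither surgery nor postpartum scan (within 0-90 days) performed", so a woman who had surgery is outside it.
- Only the first line, "Ovary normal at postpartum scan", does not depend on surgery status.

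The data forms in Appendix 5 foresee operations without removal. The complications form has the item "Underwent surgery for a mass-related incident but mass not removed". The surgery form lists cyst drainage, adhesiolysis and diagnostic laparoscopy, and has a finding for no tumour at operation.

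**The concern.** The primary outcome is the share of benign masses among those that ADNEX classifies as malignant, so each ADNEX-positive woman needs a benign or malignant reference status. For a woman operated on without histology, the protocol removes the requirement for the one remaining source of that status and gives no rule for assigning it. The outcome scan must fall within 0-90 days postpartum. Once that window has closed, the information is gone, and no later analysis decision can bring it back. Such losses are unlikely to be random, because operations that leave the mass in place tend to follow acute events. The result could be a small bias in the false discovery rate, and a set of participants whom different analysts would code differently.

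**Working it through.** **1. The outcome rules, applied to operated women.** Each combination of histology and scan result was set against the nine lines.

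| Histology of index mass | Postpartum scan | Outcome line |
|---|---|---|
| Benign (including from biopsy alone) | Any or none | Benign |
| None | Not done (waived) | None |
| None | Done anyway, certainty score 1 to 5 | None |
| None | Done anyway, ovary normal | Benign |

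The gap therefore comes from absent histology, not from leaving the mass in place: a biopsy without removal still fits. It also remains if a centre performs the scan voluntarily and the mass persists, because every certainty-score line without histology is restricted to unoperated women. A woman operated on without histology after her postpartum scan meets the same missing category, although her scan data exist.

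**2. The protocol's own precision figure** (section 8, 40% threshold). Inputs: 19 centres, 15 women per centre per year, 3 years, prevalence 8%, sensitivity 73%, specificity 95.8%.

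- n = 19 × 15 × 3 = 855; malignant = 0.08 × 855 = 68.4; benign = 786.6
- True positives = 0.73 × 68.4 = 49.93; false positives = 0.042 × 786.6 = 33.04; all positives = 82.97
- False discovery rate = 33.04 / 82.97 = 39.8%
- Half-width = 1.96 × √(0.398 × 0.602 / 82.97) = 10.5%, which agrees with the stated 11%

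This calculation makes no allowance for women without a classifiable outcome.

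**3. Size of the gap.** The protocol does not say how often surgery yields no histology. Assume 1-3% of all women, with every affected mass benign and ADNEX-positive at the planned rate of 1 − 0.958 = 0.042.

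- Women affected: 0.01 × 855 = 8.55 to 0.03 × 855 = 25.65, so about 9-26
- False positives lost: 8.55 × 0.042 = 0.36 to 25.65 × 0.042 = 1.08, about 0.4-1.1
- Observed rate at 1%: (33.04 − 0.36) / (82.97 − 0.36) = 32.68 / 82.61 = 39.6%
- Observed rate at 3%: (33.04 − 1.08) / (82.97 − 1.08) = 31.96 / 81.89 = 39.0%

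**4. Direction.** With the protocol's rounded counts (50 true and 33 false positives, 33/83 = 39.8%), losing one benign positive gives 32/82 = 39.0%, and losing one malignant positive gives 33/82 = 40.2%.

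**5. A deliberately heavier case.** If 5% of all ADNEX-positive women were lost (4.1 women, assumed), the observed rate would be 36.7% if all were benign and 41.9% if all were malignant. The half-width would be 10.8%. Precision hardly changes, so the issue is bias and completeness.

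**The case against.** The strongest reply is that surgery in this protocol means removal. The waiver stands under the item on histological diagnosis, section 6.2 refers elsewhere to the removed mass, and section 6.4 expects the tumour to be taken out. The non-removal item sits on the complications form, apart from the surgery form, so such a woman could be read as still managed conservatively and due for the postpartum scan. That is a reasonable reading of intent. It does not limit the waiver as written, however, and a centre following section 6.1 literally would not arrange the scan.

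It is also fair that the waiver does not forbid a scan, that a normal ovary on a voluntary scan gives a benign outcome, and that several listed procedures can accompany histology. These points narrow the gap but leave the persisting mass without a line.

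A reader might infer that these women are excluded from the primary analysis by rule. The protocol does not say so. Handling of missing reference outcomes may be set in an analysis plan that is not at hand. Such a plan could settle the coding, but it could not recover a scan that was never done.

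A reader might also take the Background's report of 4 of 17 operations for acute pain suggestive of torsion as a guide to frequency. It says nothing about missing histology, and the same account gives the patients' diagnoses without mentioning any operated woman who lacked one.

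**Conclusion.** The gap is real and lies in the protocol's own wording: surgery without histology of the index mass carries no required outcome scan and no outcome category, unless an unrequired scan shows a normal ovary. Its effect on the primary outcome is probably small. Under the assumed 1-3% with all masses benign, the shift is less than 1 percentage point against a half-width of about 11 points. That rests on an assumed frequency, on the planned specificity of 95.8% holding in this subgroup, and on the lost masses being benign. One might infer that the loss must flatter ADNEX because these masses were mostly thought benign. The protocol does not establish this, and losing malignant positives would raise the rate instead. The case for acting is that the loss is avoidable, permanent once the postpartum window closes, and cheap to prevent.

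**What to change.** Reconcile section 6.1 and both parts of the outcome definition in section 6.2 with the complications and surgery forms in Appendix 5. For outcome assignment only, and without touching any decision on surgery or care:

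- define operated as surgery that yields histology of the index mass;
- apply the scan waiver only where that histology exists;
- send other operated women to the existing postpartum subjective-assessment branch;
- assign uncertain where neither histology nor a postpartum scan is available;
- record any drainage or other alteration of the mass, so that these cases can be examined in a sensitivity analysis.

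The cost is a wording change and a few more postpartum scans, which the financial section of the protocol already describes as standard practice. One drawback remains: some of the masses assessed by scan will have been altered by the operation, so their subjective classification will be less secure. The sensitivity analysis is there to show whether that matters.
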